### 6.2.1 Vital Signs

Seated pulse rate and BP measurements will be performed as outlined in the Schedule of Assessments ([Appendix A](#)). Measurements will be taken with the subject sitting, having rested in this position for at least five (5) minutes. Vital signs should be taken before ECGs and other scheduled assessments.

### 6.2.2 Physical Examination

A complete PE is to include documentation of height (screening only), weight, body temperature, and vital signs (BP [sitting], pulse rate [sitting], and respiratory rate) and will be performed by a physician or staff member who is qualified to perform such examinations (e.g., physician's assistant, nurse practitioner). All PEs, whether focused on symptoms (symptom-directed) or complete, will include assessment of cardiac (including heart rate and vital signs), musculoskeletal (e.g., joints, muscles), and neurological (e.g., gait) systems.

### 6.2.3 12-Lead ECG

Twelve-lead ECGs will be performed as outlined in the Schedule of Assessments ([Appendix A](#)). ECGs will be recorded after the subject has rested in the supine position for at least 5 minutes.

The following ECG parameters will be collected: PR interval, QRS interval, RR and QTc or QTcF. The ECG findings will be evaluated by a qualified physician for the

presence of abnormalities (qualitative assessment). The physician will assess each ECG as normal, abnormal/not clinically significant, or abnormal/clinically significant.

Abnormalities in the ECG that lead to a change in subject management or result in clinical signs and symptoms are considered clinically significant for the purposes of this study and will be recorded in the AE eCRF. If ECG abnormalities meet criteria defining them as serious, they must be reported as an SAE (**Section Error! Reference source not found.**).

#### 6.2.4 Clinical Laboratory Parameters

Clinical laboratory tests will be performed as outlined in the Schedule of Assessments ([Appendix A](#)). Samples should be taken pre-dose and will be collected and assessed locally.

**Table 4 Clinical Laboratory Panels**

Hematology	Serum Chemistry	Other

White blood cell count with differential (including at minimum: neutrophils, basophils, eosinophils, lymphocytes, monocytes)

Red blood cell count

Hemoglobin

Hematocrit

Platelet count

MCV

	

Albumin

Alkaline phosphatase

ALT

AST

BUN

Calcium

Chloride

CO2

Creatinine/GFR

CPK

Total and direct bilirubin

GGT

Globulin

Glucose

HBV (screening only)

HCV (screening only)

HIV (screening only)

Lactate dehydrogenase

Magnesium

Phosphorus

Potassium

Sodium

Total protein

Uric acid

	

Whole blood tuberculin test (screening only)

Urinalysis

Abbreviations: ALT = alanine aminotransferase; AST = aspartate aminotransferase; BUN = blood urea nitrogen, CPK = creatinine phosphokinase; GFR = glomerular filtration rate; GGT = gamma glutamyl transferase; HBV = hepatitis B virus; HCV = hepatitis C virus; HIV = human immunodeficiency virus; MCV = mean corpuscular volume

Abnormalities in clinical laboratory tests that lead to a change in subject management (e.g., dose delay, requirement for additional medication or monitoring) are considered clinically significant for the purposes of this study and will be recorded on the AE eCRF page. Laboratory results will be classified using the CTCAE v5.0. If laboratory values constitute part of an event that meets criteria defining it as serious, the event (and associated laboratory values) must be reported as an SAE (see [Section Error! Reference source not found.](#)).

### 6.2.5 Pregnancy Testing

[figure not shown]
Pregnancy tests (urine) will be done in women of childbearing potential. Positive urine results are to be confirmed with serum testing. In the event of a positive urine test at baseline, serum testing results should be acquired within 48 hours prior to study start.

In the event that a subject, or subject's partner, becomes pregnant while on study, she will be monitored until the outcome of the pregnancy is known. The baby will continue to be monitored for 30 days after delivery. The data are reported on a pregnancy form within 24 hours of becoming aware.

## 7. PHARMACOKINETICS

No pharmacokinetic analysis to be performed in this study.

## 8. PHARMACODYNAMICS

## 9. SAFETY

### 9.1 SAFETY PARAMETERS

Safety data will be collected from the time the subject signs the ICF form until 28 days after their last dose of study drug (the AE reporting period). The primary safety outcome will be the percentage of subjects experiencing TEAEs and SAEs.

Safety assessments will include AEs, SAEs, PEs, vital sign measurements, clinical laboratory evaluations (hematology, chemistry, and urinalysis), and ECGs. Reasons for treatment discontinuation because of toxicity will be documented.

All AEs that occur in enrolled subjects during the AE reporting period must be recorded regardless of the relationship of the AE to study drug. Any known untoward event that occurs beyond the AE reporting period that the Investigator assesses as possibly related to study drug also should be reported to Kadmon.

Careful monitoring of all toxicities will be carried out. Vital sign measurements, including BP, pulse rate, respiratory rate, and temperature will be monitored throughout the study.

### 9.2 ADVERSE EVENT DEFINITION

An AE is defined as any untoward medical occurrence in a clinical trial subject associated with the use of a drug, whether or not considered drug related. An AE can be an unfavorable and unintended sign (e.g., an abnormal laboratory value finding), a symptom, or a disease temporally associated with the use of a drug, without judgment as to causality. An AE can arise from use of the drug (e.g., use in combination with another drug) and from any route of administration, formulation or dose, including an overdose. An AE also includes, but is not limited to, any clinically significant worsening of a pre-existing condition. Examples include:

- Any sign, symptom, physical finding, or laboratory result that has worsened in nature, severity or frequency compared to baseline
- Reactions from an investigational drug, including those occurring as a result of an overdose, abuse of the study drug, withdrawal phenomena, sensitivity, or toxicity
- Concurrent illness that was not present or worsens in nature, severity, or frequency compared to baseline
- Injury or accident; and/or

- Exacerbation of a pre-existing condition

For the purpose of data collection, all untoward events that occur after informed consent through 28 days after last dose of study drug are to be recorded on eCRFs by the investigational site.

### **9.3 EVALUATING ADVERSE EVENTS**

The Investigator will determine the seriousness, intensity, and causality of an AE associated with the use of the study drug (i.e., events where there is a reasonable possibility that the event may have been caused by the study drug) based on the definitions that follow.

#### **9.3.1 Serious Adverse Events**

The SAE definition and reporting requirements are in accordance with Title 21 Part Code of Federal Regulations (CFR) 312.32 and the Guidance for Industry and Investigators Safety Reporting Requirements for Investigational New Drug (INDs) and Bioavailability/Bioequivalence (BA/BE) Studies.

Serious adverse event assessments will be performed from the time when the ICF is signed.

**SAE:** An AE is considered "serious" if, in the view of either the Investigator or sponsor, it results in any of the following outcomes:

**Death:** This includes any death that occurs while the subject is "on study" as well as any death that occurs within 28 days after study drug discontinuation.

**Note:** Death is an outcome of an AE, and not an AE in itself. The event(s) that caused death (e.g., illness, accident) is the SAE. Death due to any other cause(s) must also be reported as an outcome of the reportable SAE.

**Life-threatening adverse event:** An AE or suspected adverse reaction is considered "life-threatening" if, in the view of either the Investigator or sponsor, its occurrence places the patient or subject at immediate risk of death. It does not include an AE or suspected adverse reaction that, had it occurred in a more severe form, might have caused death.

**Inpatient hospitalization or prolongation of existing hospitalization:** In the absence of an AE, the Investigator should not report hospitalization or prolongation of hospitalization. This is the case in the following situations:

- Hospitalization or prolongation of hospitalization is needed for a procedure required by the protocol
- Hospitalization or prolongation of hospitalization is part of routine procedure followed by study center
- Hospitalization for survey visits or annual physicals

In addition, a hospitalization planned before the start of the study for a pre-existing condition which has not worsened does not count as an SAE.

- **Persistent or significant incapacity or substantial disruption of the ability to conduct normal life functions**
- **Congenital anomaly/birth defect**
- **Important medical event:** An event that may not result in death, be life threatening, or require hospitalization may be considered serious when, based upon appropriate medical judgment, it may jeopardize the subject and may require medical or surgical intervention to prevent one of the outcomes listed in this definition.

### **9.3.2 Protocol-related Adverse Events**

Adverse events that are not study drug related may nevertheless be considered by the Investigator or the medical monitor to be related to the conduct of the clinical study. That is, the event may be related to the fact that a subject is participating in the study. For example, a protocol-related AE may be an event that occurs during a washout period or that is related to a procedure required by the protocol.

### **9.3.3 Relationship to Study Drug**

The Investigator will attempt to assess the relationship of the event to study drug using a 5-point scale (not related, unlikely related, possibly related, probably related, or definitely related) ([Appendix F](#)).

### **9.3.4 Recording Adverse Events**

All AEs (including SAEs) are to be accurately recorded on the Adverse Event page of the subject's eCRF during the subject's participation in the study. The severity of each AE will be graded using the CTCAE v5.0 scale. The date of onset as well as the end date of the event also should be recorded or the event should be entered as "ongoing". In addition, the method used to treat the AE and the outcome of the AE also will be noted. In the event that the grade of an AE worsens, an end date should be entered to the initial AE and a new AE entered with the updated grade and date of onset. The Investigator will assess the relationship of the event to study drug. Note: All SAEs also are to be entered onto an SAE form and sent to sponsor or designee.

### **9.3.5 Hospitalization**

In the absence of an AE, the Investigator should not report hospitalization or prolongation of hospitalization. This is the case in the following situations:

- Hospitalization or prolongation of hospitalization is needed for a procedure required by the protocol.
- Hospitalization or prolongation of hospitalization is part of routine procedure followed by study center.
- Hospitalization for survey visits or annual physicals.

In addition, a hospitalization for elective procedures planned before or after the start of the study for a pre-existing condition that has not worsened does not count as an SAE.

### **9.3.6 Serious Adverse Event Reporting**

#### **9.3.6.1 Governing Regulatory Requirements**

Compliance with this request for prompt reporting is essential in that the sponsor is responsible for informing the US FDA as well as all other participating Investigators of the event.

Under FDA ruling (US Code of Federal Regulations, Title 21 CFR Part 312.32) and the Guidance for Industry and Investigators Safety Reporting Requirements for INDs and BA/BE Studies, the sponsor is required to submit written documentation, in the form of an IND safety report, detailing:

- Any event associated with the use of the drug, that is both serious and unexpected, or
- Any findings from clinical, epidemiological, or pooled analysis of multiple studies or any findings from animal or *in vitro* testing that suggest a significant risk in humans exposed to the drug.

Written submission must be made by the sponsor to the FDA and the IRB/IECs as soon as possible and in no event later than 15 calendar days after the sponsor's initial notification of the event. Any unexpected death or life-threatening suspected adverse drug reaction must be reported to FDA no later than 7 calendar days after the sponsor's initial receipt of the information. The sponsor shall also inform all Investigators.

### **Time Frame for Reporting**

Any death, SAE, pregnancy (including pregnancy of a partner), experienced by a subject while receiving or within 28 days of receiving study drug, regardless of relationship to study drug, or any death that occurs more than 28 days after receiving study drug, and is believed to be study drug-related, must be promptly reported (within 24 hours of the Investigator becoming aware of the event) by e-mail to the sponsor (or designee).

Contact information for SAE reporting:

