### **1.3 BELUMOSUDIL NONCLINICAL EXPERIENCE**

In vitro, belumosudil has demonstrated an impact on the T-helper 17 (Th17) and regulatory T cells (Treg)-immune responses as well as on the actin/myosin cytoskeletal network and collagen formation. In vivo, belumosudil has demonstrated efficacy in a variety of clinically relevant animal models of disease including chronic graft versus host disease (cGVHD), scleroderma, idiopathic pulmonary fibrosis (IPF), and other autoimmune diseases.

Good Laboratory Practice (GLP) compliant rat and dog general toxicology/toxicokinetic studies of acute, subchronic (1-and 3-month), and chronic (6-month rat and 9-month dog) duration have been completed. In addition, safety pharmacology (human ether-à-go go related gene [in vitro], central nervous system [rat], respiratory [rat], and cardiovascular [dog]), embryo-fetal toxicology [rat and rabbit], male/female fertility [rat]), genotoxicity, and phototoxicity studies have also been completed. The primary nonclinical toxicology finding at/near clinically relevant exposures were limited to changes in the cardiovascular (blood pressure [BP] lowering), hepatic (transaminitis, hypertrophy/increased organ weight, and

cholestasis/inflammation), renal (increased blood urea nitrogen [BUN], tubular changes, pigmentation, intracellular protein droplets in the epithelium), gastrointestinal (decreased appetite), and hematopoietic/immunologic (anemia with regeneration and thymic/splenic lymphoid depletion) systems.

Belumosudil demonstrated embryo-fetal toxicity/teratogenicity as well as reduced male fertility (reduced fertility index/sperm concentration/motility and increased abnormal sperm percentage), and changes in the testes/epididymis (decreased organ weights and degenerative histopathology). Male fertility findings were generally at higher than clinically relevant exposures.

All pivotal non-clinical safety studies (i.e., those studies identified in International Conference on Harmonisation guidelines as needing to be conducted in accordance with GLP) were conducted in a country that is a member of the Organisation for Economic Cooperation and Development (OECD) Mutual Acceptance of Data program in accordance with the OECD Test Guidelines and Principles of GLP. Study details and potential clinically relevant findings from these studies are summarized in the belumosudil [Investigator's Brochure \(IB\)](#).

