#### 3.4 INCLUSION CRITERIA

1. Male and female subjects  $\geq$  18 years old with the diagnosis of dcSSc according to the 2013 American College of Rheumatology and European League Against Rheumatism criteria

2. Must have disease duration (defined as interval from first non-Raynaud disease manifestation) of  $\leq$  6 years
3. Must have mRSS  $\geq$  15 but  $\leq$  40
4. Must have active disease as determined by the Principal Investigator within the 6 months prior to screening
5. Adequate organ and bone marrow functions evaluated during the 28 days prior to enrollment as follows:
  - a. Absolute neutrophil count  $\geq 1.5 \times 10^9/L$
  - b. Platelet count  $\geq 100 \times 10^9/L$
  - c. Total bilirubin  $\leq 1.0 \times$  upper limit of normal (ULN)
  - d. Alanine aminotransferase (ALT), aspartate aminotransferase (AST), and serum creatinine  $\leq 1.5 \times$  ULN
6. Female subjects of childbearing potential have a negative pregnancy test at screening. Females of childbearing potential are defined as sexually mature women without prior hysterectomy or who have had any evidence of menses in the past 12 months. However, women who have been amenorrheic for 12 or more months are still considered to be of childbearing potential if the amenorrhea is possibly due to prior chemotherapy, anti-estrogens, or ovarian suppression.
  - a. Women of childbearing potential (i.e., menstruating women) must have a negative urine pregnancy test (positive urine tests are to be confirmed by serum test) documented within the 24-hour period prior to the first dose of study drug.
  - b. Sexually active women of childbearing potential enrolled in the study must agree to use two forms of accepted methods of contraception during the course of the study and for 3 months after their last dose of study drug. Effective birth control includes (i) intrauterine device plus 1 barrier method; (ii) on stable doses of hormonal contraception for at least 3 months (e.g., PO, injectable, implant, transdermal) plus 1 barrier method; or (iii) 2 barrier methods. Effective barrier methods are male or female condoms, diaphragms, and spermicides (creams or gels that contain a chemical to kill sperm), or a vasectomized partner.
7. For male patients who are sexually active and who are partners of premenopausal women: agreement to use 2 forms of contraception as in criterion number 6b above during the treatment period and for at least 3 months after the last dose of study drug.

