8. Male subjects must not donate sperm for 3 months after last dose of study drug.

---

9. Able to provide written informed consent prior to the performance of any study-specific procedures.

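### Pregnancy reporting stops 28 days after the last dose and follow-up is tied to being on study, while the protocol requires contraception for 3 months after the last dose; align the periods or explain the difference

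*Protocol*

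**What the plan says.** **Contraception period.** Protocol Section 3.4, criterion 6b, says that sexually active women of childbearing potential "must agree to use two forms of accepted methods of contraception during the course of the study and for 3 months after their last dose". Criterion 7 places the same duty on sexually active men with premenopausal partners, "during the treatment period and for at least 3 months after the last dose of study drug". The synopsis repeats both.

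**Stated hazard.** Section 1.3 reports: "Belumosudil demonstrated embryo-fetal toxicity/teratogenicity as well as reduced male fertility". It adds that the male fertility findings generally arose above clinically relevant exposures. It attaches no such qualifier to the embryo-fetal finding.

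**Reporting period.** Time Frame for Reporting, in Section 9.3.6.1, covers "Any death, SAE, pregnancy (including pregnancy of a partner), experienced by a subject while receiving or within 28 days of receiving study drug", whatever the relationship to study drug. The only extension past 28 days in that sentence is "or any death that occurs more than 28 days after receiving study drug, and is believed to be study drug-related".

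**Follow-up trigger.** Section 6.2.5 provides that if a subject or a subject's partner "becomes pregnant while on study, she will be monitored until the outcome of the pregnancy is known". The infant is then followed for 30 days after delivery. The section gives no post-dose period.

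**Last contact.** Section 5.3 and Appendix A place the final visit, with the final pregnancy test, 28 days (± 3) after the last dose.

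**The concern.** The protocol sets two post-dose periods for one hazard. For 3 months it binds subjects to contraception, which treats a conception in that time as something to prevent. After 28 days it stops asking sites to tell the sponsor if one occurs. A site that follows the text exactly could learn of a pregnancy in the second or third month after the last dose and have no duty to report it. Nor would the monitoring to outcome and the 30-day infant follow-up in Section 6.2.5 clearly be triggered.

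At stake is safety information on a drug for which the protocol states embryo-fetal toxicity, in a disease it describes as 80% to 90% female. Partners of male subjects fall in the same gap. No efficacy endpoint or sample size is affected.

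**Working it through.** The plan states no figure to reproduce. The check compares the periods and then looks for any other rule that covers the difference.

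**Step 1: length of the gap**

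Inputs: contraception period of 3 months (criteria 6b and 7); reporting period of 28 days (Section 9.3.6.1). The documents do not convert 3 months to days. I assume 91 and vary it.

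Uncovered share = (contraception period − reporting period) / contraception period

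| 3 months taken as | Uncovered days | Share |
|---|---|---|
| 84 days | 84 − 28 = 56 | 66.7% |
| 89 days | 89 − 28 = 61 | 68.5% |
| 90 days | 90 − 28 = 62 | 68.9% |
| 91 days | 91 − 28 = 63 | 69.2% |
| 92 days | 92 − 28 = 64 | 69.6% |

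If the end of coverage is taken instead as the final visit, at day 25 to 31, the share runs from 63.1% (84 days, visit at day 31) to 72.8% (92 days, visit at day 25). It exceeds half in every case.

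**Step 2: does another rule cover days 29 to 91?**

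| Rule | Reach after day 28 | Covers a pregnancy as such? |
|---|---|---|
| Section 9.3.6.1, Time Frame for Reporting | Deaths believed drug-related | No |
| Section 6.2.5 | Depends on being on study, which is not defined. The synopsis and Section 3.1 end participation with the 4-week follow-up | Not on its wording |
| Section 9.1 | Known untoward events judged possibly related | No |
| Sections 9.3.1 and 9.3.6.2 | SAEs judged possibly related; a congenital anomaly is an SAE | Only an outcome that is itself an SAE |
| Section 9.4 | Follow-up of late, possibly related SAEs | No |

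Criterion 6b names the course of the study and the 3 months after the last dose as separate items. That tells against reading the Section 6.2.5 trigger as running to 3 months. Section 9.3.6.1 also lists pregnancy apart from SAEs and requires it without a causality judgement. The late routes all require such a judgement.

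**Step 3: how many pregnancies could this involve?**

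The documents give neither the number of women of childbearing potential nor a pregnancy rate, so this is an assumed range.

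- Women enrolled, if the protocol's 80% to 90% figure for systemic sclerosis held here: 0.80 × 12 = 9.6 to 0.90 × 15 = 13.5, so about 10 to 14.
- Assumed women of childbearing potential: 3 to 14. Assumed yearly pregnancy rate under two methods: 1% to 10%.
- Expected pregnancies in 63 days = women × yearly rate × 63/365.
- Low: 3 × 0.01 × 63/365 = 0.005. High: 14 × 0.10 × 63/365 = 0.24.

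Partners of male subjects are not counted.

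**Step 4: drug remaining at the start of the gap**

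Section 1.4.1 gives a terminal half-life of about 7 hours with little or no accumulation. Day 28 is (28 × 24)/7 = 96 half-lives after the last dose.

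**The case against.** The strongest reply is that the two periods may differ on purpose. On the protocol's own half-life, a woman who conceives on day 29 or later has essentially no drug left, and no section says that the reporting and contraception periods must match. This stands as far as it goes: the gap covers a precautionary margin, not demonstrated exposure. It does not explain why the protocol treats the margin as worth two forms of contraception but not worth a report, and the documents give no reason for the difference.

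Second, a reader might infer that drug-related fetal harm after day 28 would go wholly unreported. The documents do not support that. A congenital anomaly is an SAE under Section 9.3.1. If judged possibly related, it is reportable without an end date under Section 9.3.6.2 and followed under Section 9.4. The route is real but passive: the site must hear of the event with no contact scheduled, and must then make a causality judgement.

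Third, the numbers are small. On the assumed ranges, well under one pregnancy is expected in the gap. This stands and limits the weight of the point.

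Fourth, the pregnancy form, the consent pages and some text directly after the quoted reporting sentence are not available for this review. An instruction there could narrow the gap, although nothing visible suggests one.

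**Conclusion.** The point holds as a mismatch within the protocol. Pregnancy reporting (28 days) and the follow-up trigger are shorter than the post-dose contraception period (3 months). About 63 of 91 days, 69% of that period, lie outside pregnancy reporting; the share stays between 63% and 73% over the conversions and visit days tried. This rests on reading on study as ending with the 4-week follow-up visit, and on the text available.

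Three stronger readings should be avoided.

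- The 69% is a share of calendar days. It is not the share of pregnancies, exposure or risk that would be missed.
- The mismatch does not show which period is right. The documents show only that they differ without explanation.
- A reader might also see a conflict between criterion 7 and criterion 8, which says "Male subjects must not donate sperm for 3 months after last dose of study drug". They govern different acts and share the same post-dose period. Criterion 8 is silent on the treatment period, but it does not contradict criterion 7.

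The change is worth making because it is cheap and concerns a stated reproductive hazard. It has no bearing on the efficacy results.

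**What to change.** Reconcile Section 3.4 (criteria 6b and 7), Section 6.2.5 and Time Frame for Reporting in Section 9.3.6.1:

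- Make a pregnancy of a subject or partner reportable, and followed to outcome, until the end of whatever post-dose contraception period the protocol keeps.
- In Section 6.2.5, replace the on-study trigger with that same period.
- At the 28-day visit, instruct subjects to tell the site of any pregnancy that begins within it.
- If the sponsor intends the periods to differ, state why.

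**Cost.** Protocol wording and a line in the pregnancy form instructions; no added visit or test. With the present 3-month period, the reporting line stays open about 2 months longer (63 days). A late pregnancy costs more. If a pregnancy is assumed to last about 9 months, follow-up to outcome plus 30 days for the infant runs about 10 months from conception. That ends about 10 months after the last visit for a conception just after it, and about 12 months after (10 + 2) for one at the end of the period. Capture would still depend on subjects making contact, so the change creates a duty to report but does not guarantee that every pregnancy is found.
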